9.2 Rationale for the Study

This study is being conducted to evaluate the efficacy, safety, tolerability and PK (for a subset of subjects) of SCY-078 in male and female subjects \geq 18 years of age with a documented *Candida auris* infection.

The primary efficacy endpoint of the study is global success, defined as either a complete or partial global (clinical and mycological) response. The primary endpoint will be determined at the end of treatment (EoT).^{12,13} Clinical response will be evaluated by the signs and symptoms of the infection and/or imaging scans, if applicable. Mycological response will be assessed by fungal culture and serological testing (β -(1,3)-D-glucan),¹⁴ if applicable. Recurrence will be assessed 42 days after the EoT (Week 6 Follow-up) as a secondary efficacy endpoint. Recurrence is defined as global success at EoT but re-emergence of the baseline *Candida* infection (with the same *Candida* species and involving the same site) during the post treatment follow-up.¹³

10.0 Study Objectives

10.1 Primary Objectives

• To evaluate the efficacy of SCY-078 as determined by a Data Monitoring Committee (DMC) by assessing global success (composite assessment of clinical and mycological success) at End of Treatment (EoT).

10.2 Secondary Objectives

- To evaluate the safety and tolerability of SCY-078
- To evaluate the efficacy of SCY-078 by measuring recurrence of the baseline fungal infection 42 days after EoT (Week 6 Follow up)
- To determine the efficacy of SCY-078 by measuring subject survival 42 and 84 days after Day 1 (first dose of study drug)

10.3 Exploratory Objectives

- To evaluate the efficacy of SCY-078 as determined by the DMC by assessing additional efficacy outcomes at EoT
- To evaluate the efficacy of SCY-078 as determined by the investigator by assessing select efficacy outcomes at EoT
- To determine the interpretative breakpoint of SCY-078 against *C. auris*
- To evaluate the pharmacokinetics (PK) of SCY-078 by population PK analysis (for a subset of subjects)

11.0 Study Endpoints

11.1 Primary Endpoints

• Efficacy as measured by the percentage of subjects with global success (complete or partial global response) at EoT as determined by the DMC

11.2 Secondary Endpoints

Safety and tolerability as measured by:

- Physical examination, vital signs, 12-lead electrocardiogram (ECG), safety laboratory tests, AEs and treatment discontinuations
- The percentage of subjects with treatment-emergent AEs

Efficacy as measured by:

- The percentage of subjects with a recurrence of the baseline fungal infection 42 days after EoT (Week 6 Follow up)
- The percentage of subjects surviving 42 and 84 days after Day 1 (first dose of study drug)

11.3 Exploratory Endpoints

- Percentage of subjects with complete global response at EoT, as determined by the DMC
- Percentage of subjects with partial global response at EoT, as determined by the DMC
- Percentage of subjects with stable disease at EoT, as determined by the DMC
- Percentage of subjects with progressive disease at EoT, as determined by the DMC
- Percentage of subjects with clinical success at EoT, as determined by the investigator
- Percentage of subjects with mycological success at EoT, as determined by the investigator
- Percentage of subjects with global success at EoT, as determined by the investigator
- Analysis of response by minimum inhibitory concentration (MIC) based on CLSI M27-A3 *in vitro* method
- SCY-078 plasma concentration by population PK analysis (for a subset of subjects)

12.0 Study Design

12.1 Overall Description of the Study

This is a multicenter, open-label, non-comparator, single-arm study to evaluate the efficacy, safety, tolerability and PK (for a subset of subjects) of SCY-078 in male and female subjects \geq 18 years of age with a documented *Candida auris* infection.

Subjects must have a documented candidiasis, including candidemia, caused by *Candida auris* to be considered for enrollment. Subjects are also eligible if they are receiving IV antifungal therapy for their *C. auris* infection and, in the judgment of the investigator, continued IV antifungal therapy is not feasible or desirable due to clinical or logistical circumstances. Additionally, subjects must be able to tolerate medication orally or through a nasogastric (NG) tube or percutaneous endoscopic gastrostomy (PEG) tube to be able to participate in the study.

Subjects must meet all study criteria to be eligible for inclusion. Inclusion of each subject in the study must be approved by the Sponsor prior to enrollment.

The study will be conducted at approximately 10 sites globally, and is planned to enroll and treat approximately 30 subjects.

Eligible subjects will receive an initial oral loading dose of 750 mg of SCY-078 (3 tablets of 250 mg) BID during the first 2 days of treatment and then subsequent oral doses of 750 mg QD for up to 90 days.

The study will consist of a combined Screening and Treatment Day 1 (Baseline) visit to determine subject eligibility and begin study treatment; a Treatment Day 2 visit for PK sampling (only for subjects who participate in the PK portion of the study); 2 additional scheduled treatment visits (Treatment Days 3 to 5 and Treatment Days 7 to 10) and treatment visits every 14 days thereafter (for up to a total of 90 days) to continue study treatment and perform clinical, mycological, imaging, serological and safety assessments, and to collect PK samples (only for subjects who participate in the PK portion of the study); an EoT visit to assess primary and exploratory efficacy outcomes; 1 follow-up (FU) visit 6 weeks after EoT (Week 6 Follow-up) to assess recurrence (secondary efficacy endpoint) and safety; and 2 survival visits/contacts to determine survival status (alive or deceased).

Efficacy will be assessed primarily in terms of global success (defined as a complete or partial global [clinical and mycological] response) at EoT as determined by the DMC. Secondary efficacy assessments will include recurrence (after EoT) and survival. Recurrence will be assessed by measuring recurrence of the baseline fungal infection 42 days after EoT (Week 6 FU). Survival will be determined on Day 42 and Day 84 (42 and 84 days after the Screening/Treatment Day 1 visit [first dose of study drug]). This can be an in-person visit or a phone contact, and will

document subject status only (alive or deceased). If subject is deceased, the relationship to the fungal infection will be recorded.

Complete global response, partial global response, stable disease and progressive disease at EoT as determined by the DMC will be assessed as exploratory efficacy endpoints. Global success, clinical success and mycological success at EoT as determined by the investigator will also be assessed as exploratory efficacy endpoints.

The following study procedures will be performed to assess treatment outcome: clinical signs and symptoms of candidiasis; radiological assessments including esophagoscopy and other imaging scans, as applicable (e.g., X-ray, ultrasound, CT and MRI); mycological testing (fungal cultures); and serological testing (β-(1,3)-D glucan).

PK analyses will be performed for subjects who give their consent to participate in the PK portion of the study (the PK Subset). Blood samples will be collected on Treatment Day 2 (one sample collected anytime post dosing), Treatment Days 3 to 5 (one sample collected predose on any of these days) and Treatment Days 7 to 10 (one sample collected predose on any of these days).

Subjects will be evaluated for safety throughout the study, including parameters such as physical exam, vital signs, 12-lead ECGs, safety laboratory tests (hematology, blood chemistry and urinalysis), AEs, treatment discontinuations and concomitant medications. A final safety assessment will be conducted at the Week 6 Follow-up visit (6 weeks after the EoT).

Results from the study will be analyzed against historical SoC-treated subjects, who will be selected from literature reviews and other data resources, and be based on the 2015 Infectious Diseases Society of America guidelines for the management of candidiasis.¹⁵

12.2 Blinding, Randomization and Stratification

This is an open-label study. There will be no randomization or stratification for this study.

Eligible subjects must be approved by the Sponsor for enrollment.

12.3 Study Duration

Each subject is expected to complete the study within approximately 132 days.

12.4 Number of Subjects and Centers

Approximately 10 study centers worldwide are expected to participate in subject enrollment and treatment. The study is planned to enroll and treat approximately 30 subjects.

13.0 Study Population

13.1 Inclusion Criteria

Subjects must fulfill all of the following criteria to be eligible for study admission:

- Subject is a male or female adult ≥18 years of age on the day the study informed consent form (ICF) is signed.
- 2. Subject has a documented candidiasis, including candidemia, caused by *Candida auris*. The subject is also eligible if he/she is receiving IV antifungal therapy for their *C. auris* infection and, in the judgment of the investigator, long-term IV antifungal therapy is not feasible or desirable due to clinical or logistical circumstances.

A documented candidiasis, including candidemia, caused by *Candida auris* is defined as the recovery of *Candida auris* by culture of a sample obtained within the last 7 days.

- 3. Subject is able to tolerate medication orally or through a nasogastric (NG) tube or percutaneous endoscopic gastrostomy (PEG) tube.
- 4. Subject is not pregnant and is highly unlikely to become pregnant or to impregnate a partner since he/she meets at least one of the following criteria:
 - a. Subject is a female subject who is not of reproductive potential and is eligible without requiring the use of contraception. A female subject who is not of reproductive potential is defined as one who: (1) has reached natural menopause (defined as 6 months of spontaneous amenorrhea with serum follicle-stimulating hormone levels in the postmenopausal range as determined by the local laboratory, or 12 months of spontaneous amenorrhea); (2) is 6 weeks' post-surgical bilateral oophorectomy with or without hysterectomy; or (3) has undergone bilateral tubal ligation. Spontaneous amenorrhea does not include cases for which there is an underlying disease that causes amenorrhea (i.e., anorexia nervosa).
 - b. Subject is a male subject who is not of reproductive potential and is eligible without requiring the use of contraception. A male subject who is not of reproductive potential is defined as one whom has undergone a successful vasectomy. A successful vasectomy is defined as (1) microscopic documentation of azoospermia, or (2) a vasectomy more than 2 years ago with no resultant pregnancy despite sexual activity post vasectomy.
 - c. Subject is a male or female subject who is of reproductive potential and agrees to remain abstinent or use (or have his/her partner use) 2 acceptable methods of contraception starting from the time of consent through 28 days after the completion of study therapy. Acceptable methods of birth control are intrauterine device, condom, hormonal contraceptives and vasectomy.

It is not yet known if the use of SCY-078 reduces the efficacy of hormonal contraception (including but not limited to oral, injectable, or implantable methods). Therefore, hormonal contraception should not be used without a second study acceptable method of birth control.

Note: Women of childbearing potential must have a negative serum pregnancy test (β -human chorionic gonadotropin [β -hCG]) prior to enrollment (performed by the site's local laboratory).

- 5. Subject and/or legal representative is/are able to understand and sign a written ICF, which must be obtained prior to treatment and any study-related procedures.
- 6. Subject and/or legal representative is able to understand and sign a consent or authorization form, which shall permit the use, disclosure and transfer of the subject's personal health information (e.g., in the US, a Health Information Portability and Accountability Act Authorization form).
- 7. Subject and/or legal representative is able to understand and follow all study-related procedures including study drug administration.

13.2 Exclusion Criteria

A subject will be excluded from participation in the study if he or she meets any of the following exclusion criteria:

- 1. Subject has a fungal disease with central nervous system involvement.
- 2. Subject has a fungal disease of the bone and/or joint that is expected to require >90 days of study drug treatment.
- 3. Subject has an inappropriately controlled fungal infection source (e.g. persistent catheters, devices, identified abscess) that is likely the source of the fungal infection.
- 4. Subject is hemodynamically unstable and/or requiring vasopressor medication for blood pressure support.
- 5. Subject has abnormal liver test parameters: AST or ALT >10 x ULN and/or total bilirubin >5 x ULN.

Note: Subjects with unconjugated hyperbilirubinemia with diagnosis of Gilbert's disease are not excluded.

- 6. Subject has an Apache score >16.
- 7. Subject has serum creatinine >3 times from Baseline (Screening/Treatment Day 1) value.

- 8. Subject has a prolonged QTcF interval (Fridericia's correction: $QTc = QT/(RR)^{0.33}$) >480 ms on the baseline ECG or other abnormalities deemed clinically significant by the investigator that would put the subject at unacceptable risk for participation in the study.
- 9. Subject requires treatment with the prohibited medications listed in Section 23.1 (Appendix A), during the following timeframes:
 - a. Select strong time-dependent CYP3A4/5 inhibitors and CYP3A4/5 inducers during the 14 days prior to enrollment and during study treatment
 - b. Select strong and moderate reversible CYP3A4/5 inhibitors during the 48 hours prior to enrollment and during study treatment
 - c. Select P-gp substrates during the 48 hours prior to enrollment and during study treatment
- 10. Subject is pregnant or lactating.
- 11. Subject has any other condition or laboratory abnormality that, in the judgment of the investigator, would put the subject at unacceptable risk for participation in the study or may interfere with the assessments included in the study.
- 12. Subject has a known hypersensitivity to SCY-078 or any of the components of the formulation.
- 13. Subject has participated in any other investigational study within at least 30 days (or 5.5 halflives of the investigational product) before signing the ICF.
- 14. Subject has received prior treatment with the study drug in a previous trial.
- 15. Subject is an employee of SCYNEXIS, Inc., the investigator or the Contract Research Organization (CRO) involved in the study, or is an immediate family member (partner, offspring, parent, sibling, or sibling's offspring) of an employee involved in the study.
- 16. Subject or legal representative is unable to provide written informed consent for any reason.
- 17. Subject is unlikely to comply with protocol requirements.

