16.2 Inclusion and Exclusion Criteria

All inclusion and exclusion criteria will be reviewed at Screening/Treatment Day 1 (prior to study treatment) to ensure that the subject qualifies for the trial.

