16.13 Safety Laboratory Tests

Safety laboratory tests (hematology, blood chemistry and urinalysis) will be measured at Screening/Treatment Day 1 (prior to study treatment), at Treatment Days 7 to 10, every 14 days

SCYNEXIS, Inc.	IND #107,521
PROTOCOL SCY-078-305	Version 0.1

thereafter up to EoT if clinically indicated, at EoT, at the Week 6 Follow-up if clinically indicated, and at unscheduled visits if clinically indicated. These may also be done more frequently as follow up to a laboratory abnormality.

The following laboratory parameters will be determined:

Hematology

• White blood cell (WBC) count

• Red blood cell (RBC) count

HemoglobinHematocrit

- Platelet count
- Differential WBC count will include percentages for segmented neutrophils, lymphocytes, monocytes, eosinophils and basophils, and absolute counts for neutrophils, lymphocytes, atypical lymphocytes, monocytes, eosinophils and basophils.

Blood Chemistry

- Sodium
- Potassium
- Alkaline Phosphatase
- Chloride
- Blood urea nitrogen (BUN)
- Creatinine
- Total creatine phosphokinase (CPK)
- Aspartate aminotransferase (AST/SGOT)
- Alanine aminotransferase (ALT/SGPT)
- Gamma glutamyl transferase (GGT)
- Lactate dehydrogenase (LDH)
- Bilirubin (total, direct, and indirect)
- Total protein

Coagulation test

- Prothrombin time (PT)
- Activated partial thromboplastin (aPTT)
- Thrombin time (TT)
- D-dimer

- Glucose
- Albumin

- Appearance (clarity, color)
- Specific gravity
- ∎ pH
- Blood
- Bilirubin

- Glucose
- Ketones
- Protein
- Leukocytes
- Urobilinogen

Reflex Microscopic Evaluation

- Bacteria

MucousRBCWBC

- CastsCrystals
- Epithelial cells

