20.3 Subject Disposition, Discontinuation, and Baseline Data

Subject disposition in terms of the number and percentage of subjects enrolled by site will be tabulated. The number of subjects enrolled, number completing the study and reasons for discontinuation will be summarized. Subject demographics and baseline characteristics such as age, race, ethnicity, sex, weight, height, body mass index, country and other relevant parameters will be tabulated.

Baseline is defined as the last non-missing assessment prior to the date (and time if appropriate) of the first dose of study drug. Change from baseline is defined as:post-baseline value – baseline value.

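### Exclusion criterion 7 compares serum creatinine with the same Screening/Day 1 value used to judge eligibility, so with the one scheduled pre-dose draw it excludes no one.

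*Protocol*

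**What the plan says.** Criterion 7 in Protocol 13.2 reads "Subject has serum creatinine >3 times from Baseline (Screening/Treatment Day 1) value". The synopsis (Protocol 7.0) carries the same wording among its KEY exclusion criteria, so this is not a slip in one place.

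The surrounding sections fix when that value is obtained:

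- Protocol 12.1 describes a "combined Screening and Treatment Day 1 (Baseline) visit to determine subject eligibility and begin study treatment".
- Protocol 16.2 has all entry criteria checked at that visit, before any study drug is given.
- Protocol 16.13 and Table 1 schedule chemistry, which includes creatinine, at that visit before dosing. The next scheduled draw is at Treatment Days 7 to 10. Extra tests are allowed to follow up an abnormality.
- Table 1 gives the visit a window of Day -1 to Day 1.
- For analysis, Protocol 20.3 states: "Baseline is defined as the last non-missing assessment prior to the date (and time if appropriate) of the first dose of study drug".

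By contrast, criterion 5 sets its liver limits against an outside reference: "AST or ALT >10 x ULN and/or total bilirubin >5 x ULN".

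**The concern.** A relative-change rule needs two values taken at different times, or one value and an outside reference. Criterion 7 names the screening value as its reference, and that is also the value available when eligibility is decided. A rule that the protocol lists as KEY would then let every candidate through on the scheduled data.

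Two things are at stake. First, SAP 5.3 lists any exclusion criterion that a subject met. An absence of criterion 7 entries would look as if subjects had passed a renal screen, when the scheduled procedure could not have identified a failure. Second, a site that notices the problem has to choose its own reference value, so sites may apply the rule differently.

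**Working it through.** The plan gives no figure to reproduce. The check is whether the rule can be met by the data that the schedule provides.

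**Inputs.** Threshold: ratio greater than 3 (Protocol 13.2, criterion 7). Reference: the Screening/Treatment Day 1 value (same place). Scheduled pre-dose creatinine draws: one (Protocol 16.13, Table 1). Window for an unscheduled repeat: Day -1 to Day 1 (Table 1).

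**Case 1: the one scheduled draw, value C.** Tested value = C and reference = C.

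Ratio = C / C = 1.0 for every C > 0. Since 1.0 is never greater than 3, no one is excluded, whatever the level.

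**Case 2: an unscheduled second pre-dose draw, with values D-1 (first) and D1 (last).** The text does not say which is Baseline, so there are two readings.

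- Reading A, first draw as reference: D1 / D-1 > 3, which requires a rise of more than 200%.
- Reading B, last pre-dose draw as reference, borrowing the analysis definition in 20.3: D1 against itself is 1.0, so only the first draw can be tested. D-1 / D1 > 3 requires a fall of more than 1 − 1/3 = 66.7%.

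Illustrative values in mg/dL (assumed, not from the documents):

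| D-1 → D1 | Reading A | Reading B |
|---|---|---|
| 6.0 → 6.0 | 1.0, not excluded | 1.0, not excluded |
| 1.0 → 6.0 | 6.0, excluded | 0.17, not excluded |
| 6.0 → 1.9 | 0.32, not excluded | 3.16, excluded |

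In the second and third rows the readings give opposite decisions on the same pair. A stable value passes under both.

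**Other entry controls.** Criterion 4 excludes hemodynamic instability or vasopressor use. Criterion 6 excludes an Apache score above 16. Criterion 11 covers a candidate for whom "Subject has any other condition or laboratory abnormality that, in the judgment of the investigator, would put the subject at unacceptable risk". Protocol 12.1 adds that "Inclusion of each subject in the study must be approved by the Sponsor prior to enrollment". None of them states a creatinine limit, and I found no creatinine, eGFR or dialysis limit for entry anywhere else.

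**The case against.** The best case for leaving this alone has four parts.

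*The rule can fire.* Repeat testing is allowed and the visit spans Day -1 to Day 1, so it would be wrong to say that criterion 7 can never operate. That stands, and the finding is limited to the single scheduled draw. But a repeat draw catches only a more than 3-fold change in about a day, in a direction the text leaves open.

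*Earlier routine-care values may exist.* Candidates may already be on IV antifungals, so older creatinine results are plausible, although the documents do not mention them. They do not rescue the rule. The wording fixes the Screening/Day 1 value as the reference, so an older result could only be the tested value. The rule would then exclude a patient whose creatinine had fallen.

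*Patients are not unguarded.* Criteria 4, 6 and 11 and Sponsor approval of each subject all remain. That stands. A reader might infer that patients with severe renal impairment entered unchecked, and the documents do not support that. Nor is renal status hidden: creatinine is in the chemistry panel, and SAP 8.2 tabulates laboratory results and flags out-of-range values in listings.

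*The study is descriptive, with about 30 subjects, and no result is shown to change.* That also stands. It limits the size of the point, but it does not make a listed KEY criterion work. It is also fair to say that even a working ratio rule would not certify absolute renal function. The narrower complaint is that an absence of criterion 7 entries shows no screening of any kind when there was one draw.

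**Conclusion.** The point holds for the scheduled procedure. With one pre-dose creatinine value the ratio is 1.0 and criterion 7 excludes no one at any level. With two pre-dose values it needs a rise of more than 200% or a fall of more than 66.7%, depending on which is called Baseline. The number of subjects affected is unknown and may be zero, since the documents give neither the number screened nor any creatinine values.

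Two stronger inferences should be resisted. One is that efficacy or safety results are biased; nothing in the documents shows this. The other is that the trial needs a renal limit. The protocol gives no renal-elimination or renal-toxicity reason for one, and Protocol 9.1 describes metabolism as mainly oxidative. The finding is that the stated rule does not do its job, and the documents do not say what was intended.

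This assumes that the protocol text reviewed here is the one that governed entry. SAP 5.3 places the entry criteria in protocol sections 11.1 and 11.2, whereas here they are in 13.1 and 13.2. That may be a slip or may point to another version. The point deserves correction because the rule is wrong as written and cheap to put right.

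**What to change.** The documents do not state whether enrolment is open, so both cases are given.

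**If enrolment is open.** In Protocol 7.0 and 13.2, anchor criterion 7 to an outside reference on the pre-dose sample, in the form criterion 5 already uses: serum creatinine above a stated multiple of ULN. The multiple is for the Sponsor to choose. 3 x ULN is only an example and has no source in the documents. If an on-treatment rule was intended, delete the criterion from 7.0 and 13.2 and add creatinine above 3 times Baseline to the discontinuation criteria in 13.3. The Sponsor should then accept explicitly that entry has no numeric creatinine limit.

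Cost: a wording change in two places, or two deletions and one added line. With the ULN form a few candidates may become ineligible; the documents do not allow a count.

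**If enrolment is closed.** Do not amend. State in the CSR that criterion 7 could not exclude any subject with a single pre-dose creatinine value, so the absence of criterion 7 entries in the SAP 5.3 listing is not evidence of a renal screen. Refer the reader to the baseline creatinine values listed under SAP 8.2. Apply no post hoc limit, reclassify no one and leave the PP population as it is.

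Cost: one or two sentences and no new output.
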